9.1. Primary Outcome

The proportion of levels achieving arthrodesis at 12 months (+/- 3 months) will be summarized as a percentage and 95% confidence interval, based on the Wilson score method for binomial confidence intervals. Integrity Implants engineering to determine if the criteria for success was met.

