4.2. Primary Outcome

Proportion of subjects with radiographic arthrodesis at 12 months +/- 3 months as determined using plain radiographic images with assessment based on the Bridwell-Lenke grading system [Bridwell and Lenke et al, 1995].

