5.1. Not applicable

6. SAMPLE SIZE:

6.1. The primary outcome of this study, radiographic arthrodesis, is commonly observed in approximately 80-100% of study subjects for TLIF/PLIF surgeries [FlareHawk CER-00001 Rev C]. With 100 subjects included, if an 88% fusion rate is observed, the 95% confidence interval for fusion success will be 80.2%-93.0%, placing the performance results within the anticipated range. Further, the inclusion of at least 100 subjects will enable the likely detection of adverse events that have a probability of occurrence of at least 1.6%, assuming a power of 80% [MedDev 2.7.1, rev 4]. This detection rate is adequate for this device and study based on the severity and frequency of anticipated adverse events associated with the FlareHawk device [FlareHawk CER-00001 Rev C]. The target sample size for inclusion will be 118 patients, assuming that up to 15% will not have data at the 12 months follow-up, yielding at least 100 patients with data.

7. ACCEPTANCE CRITERIA:

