7.1. Inclusion Criteria

Subjects must meet all of the inclusion criteria to be included in this study.

To be a part of this study, the subject must:

- Have been at least 18 years of age and skeletally mature at the time of surgery
- Have had clinical and radiological evidence of degenerative disc disease of the lumbar spine
- Have been treated with PLIF or TLIF surgery using the FlareHawk expandable interbody cage(s) at 1 or 2 contiguous levels from L2 to S1

	Clinical Protocol	Doc: CP-00001	Rev C
	Transforaminal/Posterior Lumbar Interbody Fusion with the FlareHawk® Expandable Interbody Fusion Device: A Retrospective Chart Review Study	Page 4 of 6	

- Have been treated using the FlareHawk expandable interbody fusion cage, according to the approved labeling, between December 1, 2017, and May 31, 2018

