3.6 Sample Size Justification

The primary outcome of this study, radiographic arthrodesis, is commonly observed in approximately 80-100% of study subjects for TLIF/PLIF surgeries [FlareHawk CER-00001 Rev C]. With 100 subjects included, if an 88% fusion rate is observed, the 95% confidence interval¹ for fusion success will be 80.2%-93.0%, placing the performance results within the anticipated range. Further, the inclusion of at least 100 subjects will enable the likely detection of adverse events that have a probability of occurrence of at least 1.6%, assuming a power of 80% [MedDev 2.7.1, rev 4]. This detection rate is adequate for this device and study based on the severity and frequency of anticipated adverse events associated with the FlareHawk device [FlareHawk CER-00001 Rev C]. The target sample size for inclusion will be 118 patients, assuming that up to 15% will not have data at the 12 months follow-up, yielding at least 100 patients with data.

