Please complete all columns below if additional Adverse Events are recorded.

Other Adverse Events (Describe event below)	Onset Date MM/DD/YYYY	Resolution Date MM/DD/YYYY	Severity 1- None 2- Mild 3- Moderate 4- Severe 5- Death	Relatedness 1- Device related 2- Procedure related 3- Not related	Action Taken 1- None 2- Medication/ Therapy 3- Revision Surgery 4- Additional Surgery 5- Other	Outcomes 1- Resolved 2- Ongoing at 12-month (+/- 3 month) Follow-up 3- Unknown
	/ /	/ /				
	/ /	/ /				
	/ /	/ /				
	/ /	/ /				
	/ /	/ /				

Clinical Site Number: Subject Number:

Case Report Form
Integrity Implants FlareHawk® Study
Radiographic Reviewer

CRF TO BE COMPLETED BY RADIOGRAPHIC REVIEWER ONLYDATE OF X-RAY: / /
MM DD YYYY**RADIOGRAPHS**X-ray views evaluated (check all that apply): AP Lateral Flexion/Extension **RADIOGRAPHS**

Using the Bridwell-Lenke grading system, what is the X-ray fusion status at L2 - L3?	Grade 1	
	Grade 2	
	Grade 3	
	Grade 4	
NA – Subject not implanted with FlareHawk device at L2-L3		

Using the Bridwell-Lenke grading system, what is the X-ray fusion status at L3 – L4?	Grade 1	
	Grade 2	
	Grade 3	
	Grade 4	
NA – Subject not implanted with FlareHawk device at L3-L4		

Using the Bridwell-Lenke grading system, what is the X-ray fusion status at L4 – L5?	Grade 1	
	Grade 2	
	Grade 3	
	Grade 4	
NA – Subject not implanted with FlareHawk device at L4-L5		

Using the Bridwell-Lenke grading system, what is the X-ray fusion status at L5- S1?	Grade 1	
	Grade 2	
	Grade 3	
	Grade 4	
NA – Subject not implanted with FlareHawk device at L5-S1		

Was any magnification adjustment used by the radiographic reviewer to grade fusion status? Yes No

If "Yes", describe below: _____

APPROVAL

Reviewer Signature: _____

Date: _____

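### The primary outcome and its precision are defined per subject, but the only planned primary analysis counts levels

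*Combined protocol and SAP*

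**What the plan says.** **Outcome.** Section 4.2 and Attachment A 3.3 give the primary outcome as "Proportion of subjects with radiographic arthrodesis at 12 months +/- 3 months as determined using plain radiographic images". The Attachment A study summary uses the same unit.

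**Precision.** Section 6 states: "With 100 subjects included, if an 88% fusion rate is observed, the 95% confidence interval for fusion success will be 80.2%-93.0" percent. Attachment A 3.6 repeats the figure. Both set it against a fusion rate of roughly 80-100%, also expressed per study subject.

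**Analysis.** Section 9.1 and Attachment A 6.2 plan one primary summary: "The proportion of levels achieving arthrodesis at 12 months (+/- 3 months) will be summarized as a percentage and 95% confidence interval", with the interval "based on the Wilson score method for binomial confidence intervals".

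**Levels per subject.** Inclusion criterion 3 (7.1 and Attachment A 3.9) reads: "Have been treated with PLIF or TLIF surgery using the FlareHawk expandable interbody cage(s) at 1 or 2 contiguous levels from L2 to S1". The radiographic reviewer's case report form asks a separate question for each of L2-L3, L3-L4, L4-L5 and L5-S1, each beginning "Using the Bridwell-Lenke grading system, what is the X-ray fusion status at". It has no field for a subject-level result. Attachment A 6.1 counts grades 1-2 as fused and 3-4 as not fused, but does not say how two levels combine.

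**The concern.** Subjects and levels are the same unit only if every included patient has one treated level, and eligibility allows two. Three things follow.

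- The declared outcome has no analysis. A subject rate would need a combination rule chosen later, possibly with the grades already known.
- A level rate would be read against a range and a precision statement that are both per subject.
- A plain binomial interval on levels treats two discs in the same patient as independent. If fusion is positively correlated within a patient, that interval is too narrow.

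A reader given 88% fused could not tell whether this meant patients or discs. Section 9.1 also leaves the success decision to the sponsor's engineering function, and the available text gives no numerical criterion. That makes it more important to fix the unit beforehand.

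**Working it through.** **1. Reproduce the plan's figure.** Wilson interval, x = 88, n = 100, z = 1.96 (z² = 3.84):

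- centre = (0.88 + 3.84/200) / (1 + 3.84/100) = 0.8659
- half-width = 1.96 × √(0.88 × 0.12/100 + 3.84/40,000) / (1 + 3.84/100) = 0.0641
- interval = 80.2% to 93.0%

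This matches section 6. The arithmetic is right, but for 88 of 100 subjects.

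**2. Inputs the documents do not give (assumed ranges).** Two-level share t = 10%, 30%, 50%. Within-patient correlation of fusion ρ = 0 or 0.5. Equal fusion probability p at every level. A subject is fused only if all treated levels are fused. 100 subjects have data, so there are 100(1 + t) = 110, 130 or 150 levels.

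**3. Relation between the two rates.**

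S = (1 − t)p + t[p² + ρp(1 − p)], so the gap is p − S = t·p(1 − p)(1 − ρ).

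Example with p = 0.88, t = 0.5, ρ = 0: gap = 0.5 × 0.1056 = 5.3 points.

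**4. Taking 88% as the level rate.**

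| t | ρ | Subject rate | Subject Wilson lower limit | Level Wilson interval |
|---|---|---|---|---|
| 10% | 0 | 86.9% | 79.0% | 80.6-92.8% |
| 10% | 0.5 | 87.5% | 79.6% | 80.6-92.8% |
| 30% | 0 | 84.8% | 76.5% | 81.3-92.5% |
| 30% | 0.5 | 86.4% | 78.3% | 81.3-92.5% |
| 50% | 0 | 82.7% | 74.1% | 81.8-92.3% |
| 50% | 0.5 | 85.4% | 77.1% | 81.8-92.3% |

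In every row the subject lower limit is below 80% and the level lower limit is above it.

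**5. Taking 88% as the subject rate, as section 6 does.** Solve S = 0.88 for p. For t = 0.3, ρ = 0: 0.3p² + 0.7p − 0.88 = 0, so p = 90.6%. Over the six scenarios the level rate is 88.5% to 91.8%. The level interval runs from 81.2-93.2% (t = 10%, ρ = 0.5) to 86.3-95.2% (t = 50%, ρ = 0), against the stated 80.2-93.0%.

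**6. Dependence on the fusion rate.** The gap is 0.5-5.3 points at 88% of levels fused, 0.4-3.7 at 92% and 0.2-2.4 at 95%. It is zero if no subject has two levels.

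**7. Direction.** The level rate is expected to be the higher one, but not always. If 12 of 30 two-level subjects fail at both levels and everything else fuses, subjects are 88/100 and levels are (130 − 24)/130 = 81.5%. In 400,000 simulated trials per scenario at p = 0.88, the level rate fell below the subject rate in 0-19%. The 19% is at t = 10%, ρ = 0.5, where the expected gap is only 0.5 points.

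**8. Coverage of the nominal 95% level interval (same simulations).** About 94% at ρ = 0 for all three shares. At ρ = 0.5 it is about 93%, 91% and 90% for t = 10%, 30% and 50%.

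**9. Level interval allowing for clustering.** Design effect = [(1 − t) + 2t(1 + ρ)]/(1 + t). At t = 0.3, ρ = 0.5 this is 1.6/1.3 = 1.231, the effective number of levels is 130/1.231 = 105.6, and 88% gives 80.4-92.9%.

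**The case against.** The strongest reply is that little depends on this. The study is a single-arm chart review with a descriptive percentage, and the available text shows no comparator, no test on fusion and no numerical pass mark. Level grades are collected, so a subject rate could still be derived. The sizes rest on an undocumented two-level share, correlation and combination rule. The extremes also do not occur together: the 5.3-point gap needs zero correlation, where coverage is about 94%, while coverage of 90% needs correlation 0.5, where the gap at the same 50% share is 2.6 points. The reversal example is very unlikely under the model used here: at p = 0.88 and ρ = 0.5, 12 or more double failures among 30 has a chance of about 2 in 10 million. Finally, 100 subjects remain adequate: at an observed 88% the level interval is no wider than stated, and after adjustment for clustering at 30% two-level it is practically the same (step 9).

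Much of this stands. The width effect is modest, the sample size is not too small, and the example shows only that the direction is not guaranteed. Some pages were not available for this review, so a combination rule elsewhere cannot be excluded, although the outcome, fusion-assessment, analysis and reviewer-form sections contain none. None of this removes the contradiction. The definition and the analysis of the only primary outcome name different units, and deriving a subject rate afterwards is the unplanned choice that a plan should prevent.

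**Conclusion.** The concern holds and should be corrected before analysis. The stated 80.2%-93.0% is computed correctly for subjects, but the planned analysis would report something else as soon as any two-level subject is included. Under the assumptions in step 2, the two rates differ by 0.5-5.3 points when 88% of levels fuse, and by less at higher fusion rates. Nominal 95% coverage of the level interval falls to about 90% in the least favourable scenario. The lower limits fall on opposite sides of 80%, but the documents present 80% as the bottom of a commonly observed range, not as a success threshold. The defect is therefore an ambiguous headline estimate, not a demonstrated change in a pass/fail result. That the units conflict rests on the text alone and needs none of these assumptions.

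**What to change.** - In 4.2 and Attachment A 3.3, state how two levels give one subject result, for example fused only if every treated level is grade 1-2.
- In 9.1 and Attachment A 6.2, make the proportion of subjects fused, with a Wilson interval, the primary analysis. The existing 80.2%-93.0% then applies unchanged.
- Report the proportion of levels as secondary, with an interval that allows for clustering within patient (GEE or cluster-robust, or Wilson on the effective number of levels).

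If the sponsor intends a level outcome instead, then 4.2, Attachment A 3.3, the study summary and both sample-size sections need rewriting per level, and the primary interval must allow for clustering.

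The cost is wording. The reviewer form already records each level, so no further data are needed. The headline rate may be a few points less favourable.

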Radiographs will be evaluated by up to three reviewers (two primary reviewers and an adjudicator, as necessary, to evaluate any contradicting reviews by the primary reviewers). Reviewers will be 3rd party board-certified orthopedic surgeons, neurosurgeons, or radiologists.

Fusion status will be determined according to the Bridwell-Lenke grading system [Bridwell and Lenke et al, 1995], with grades 1-2 accepted as “Fused” and grades 3-4 accepted as “Not Fused”:

- Grade 1: Fused with remodeling and trabeculae present
- Grade 2: Graft intact, not fully remodeled and incorporated, but no lucency present
- Grade 3: Graft intact, potential lucency present at top and bottom of graft
- Grade 4: Fusion absent with collapse/resorption of the graft

6.2 Data Analysis:

Primary outcome:

The proportion of levels achieving arthrodesis at 12 months (+/- 3 months) will be summarized as a percentage and 95% confidence interval, based on the Wilson score method for binomial confidence intervals.

Secondary outcomes:

Continuous variables, such as baseline demographics and change in patient-reported outcomes from preoperative baseline to 12 months, will be summarized using mean, standard deviation, minimum and maximum values. Paired t-test or a non-parametric equivalent (if data does not satisfy assumptions of normality) will be used to determine if changes in VAS or ODI scores are statistically significant from preoperative baseline to 12 months (+/- 3 months) follow-up. Responder analyses for changes in patient-reported outcomes at 12 months (+/- 3 months) will be conducted using minimum clinically important differences (MCID). Significant clinical improvements from preoperative baseline to 12 months (+/- 3 months) follow-up will be determined on a per-patient basis using the following MCID values:

- Improvement in ODI \geq 10 points [Ostelo et al. 2008]
- Improvement in VAS leg pain \geq 15 points [Ostelo et al. 2008]
- Improvement in VAS back pain \geq 15 points [Ostelo et al. 2008]

The proportion of patients with improvements exceeding the MCID values will be summarized as a percentage and 95% confidence interval.

Sub-group analyses will be performed based on the implant version (split-shim vs. “Version B”), history of previous surgery at the index level, patient co-morbidities, and demographic variables.

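### Section 9.1 calls for a success verdict on fusion by the sponsor's engineering group, but the available text gives no study-level criterion for that verdict

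*Combined protocol and SAP*

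**What the plan says.** The primary outcome is defined per subject in section 4.2 and Attachment A 3.3: "Proportion of subjects with radiographic arthrodesis at 12 months +/- 3 months". The analysis in section 9.1 and Attachment A 6.2 counts levels: "The proportion of levels achieving arthrodesis at 12 months (+/- 3 months) will be summarized as a percentage and 95% confidence interval". The interval is to be a Wilson interval.

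Section 9.1 then adds a decision that Attachment A 6.2 does not contain: "Integrity Implants engineering to determine if the criteria for success was met".

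The places where a criterion might be expected are these:

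- **Section 7**, headed "7. ACCEPTANCE CRITERIA", contains only inclusion criteria (7.1) and exclusion criteria (7.2).
- **The hypothesis** (section 4.1; Attachment A 3.1) expects fusion but names no rate.
- **The sample-size text** (section 6.1; Attachment A 3.6) says that arthrodesis "is commonly observed in approximately 80-100% of study subjects for TLIF/PLIF surgeries". It illustrates precision with 88 fusions in 100 subjects and describes the resulting interval as "placing the performance results within the anticipated range". It does not call this a success criterion, and section 9.1 does not refer to it.
- **Attachment A 6.1** fixes which Bridwell-Lenke grades count as fused. That defines fusion for a level, not success for the study.

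**The concern.** A plan that announces a pass/fail verdict on its primary outcome needs to state the pass mark, the statistic it applies to and the unit. Here the verdict is assigned to a group within the manufacturer, and none of the three is given where the verdict is described.

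The choice of statistic matters. If the estimate must reach 80%, the pass mark is 80 in 100. If the lower confidence limit must reach 80%, it is 88 in 100. A result between those counts would be a success under one rule and not under the other.

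Timing adds to the need for a written rule. The study is retrospective. The last surgery date in the section 4.4 window is May 31, 2018. Adding 15 months (12 + 3) gives August 31, 2019, which is before the November 15, 2019 date on the protocol. Follow-up films for that window would therefore already exist, and a rule is clearly prespecified only if it is written before those films are graded.

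**Working it through.** **Inputs.** From section 6.1: n = 100 subjects with data, an illustrative 88% fusion rate, and a reference range of about 80-100%. From section 9.1: the Wilson 95% interval. Assumption: independent subjects with one fused/not-fused outcome each.

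**Step 1: reproduce the plan's interval.** With z = 1.96, the Wilson limits are

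[p + z²/(2n) ± z·√(p(1−p)/n + z²/(4n²))] / (1 + z²/n).

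For p = 0.88 and n = 100:

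- centre = (0.88 + 0.0192)/1.0384 = 0.8659
- half-width = 1.96 × √(0.001056 + 0.000096)/1.0384 = 0.0641
- limits = 80.2% and 93.0%, which match the plan.

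**Step 2: pass mark if the lower limit must reach 80%.** The Wilson lower limit reaches 0.80 exactly when p ≥ 0.80 + 1.96 × √(0.80 × 0.20/100) = 0.80 + 1.96 × 0.04 = 0.8784. The smallest passing count is therefore 88 of 100. As a check, the lower limit is 80.19% for 88/100 and 79.02% for 87/100. The plan's own example is the smallest passing result under this rule.

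**Step 3: pass mark if the point estimate must reach 80%.** The smallest passing count is 80 of 100, with a Wilson interval of 71.1% to 86.7%.

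**Step 4: chance of declaring success.** This is the exact binomial tail, P(X ≥ r) = Σ C(100, k) pᵏ(1−p)¹⁰⁰⁻ᵏ for k = r to 100.

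| True fusion rate | Lower limit ≥ 80% (r = 88) | Estimate ≥ 80% (r = 80) |
|---|---|---|
| 75% | 0.1% | 14.9% |
| 80% | 2.5% | 56.0% |
| 88% | 57.6% | 99.3% |
| 90% | 80.2% | 99.9% |

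**Step 5: an example between the two marks.** An observed 82/100 has a Wilson interval of 73.3% to 88.3%. It passes on the estimate and fails on the lower limit.

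**The case against.** The strongest reply is that the rule is already implied. The sample-size text places a whole interval, 80.2% to 93.0%, inside the 80-100% range, and 88 is the smallest count for which the lower limit clears 80%. This is a good argument for the lower-limit reading, and it stands as the most natural one. It does not close the matter, because the text justifies precision, is not linked to section 9.1, and speaks of performance results in a way that an estimate of 80% or more could also satisfy.

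Second, this is a single-arm chart review whose primary analysis is an estimate with an interval. No test is planned, so an uncontrolled false-success rate is a weaker complaint than it would be in a confirmatory trial. That is fair. The point arises only because one sentence promises a verdict.

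Third, discretion is limited. Third-party physicians grade the films, with adjudication, the grade cut-off is fixed, and the percentage and interval will be reported whatever the verdict. This stands. Only the success label is open.

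Fourth, text between the heading of section 8 and section 9.1 was not in the copy available for this review. A criterion there cannot be excluded, so the point is limited to the available text.

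A reader might go further in two ways that the documents do not support:

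- One is to infer that mere overlap with 80-100% would count as success, which 73/100 would meet. Its interval, 63.6% to 80.7%, lies mostly below 80% and cannot naturally be described as "placing the performance results within the anticipated range".
- The other is to infer that success will be fixed once the fusion rate is known. Section 9.1 says who judges whether the criteria were met. It does not say when the criteria are set.

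**Conclusion.** The point holds in a limited form. Section 9.1 provides for a success verdict, and the available text does not state the threshold, the statistic or a consistent unit for it. The two readings that the sample-size text allows differ by 8 subjects in 100 (88 against 80). At a true rate of 80% they differ in the chance of success from 2.5% to 56%.

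These figures assume 100 evaluable, independent subjects with one outcome each. They would change if levels were the unit, because two levels in one subject need not be independent. The size of the gap shows what is left undecided. It is not evidence that any rule has been chosen to suit a result, and it does not affect the reported estimate or its interval.

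**What to change.** Before image review, replace the engineering sentence in section 9.1 and add the same text to Attachment A 6.2, which at present has no success sentence:

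> Success: the lower limit of the two-sided 95% Wilson interval for the proportion of subjects fused (all treated levels grade 1-2) is at least 80%; otherwise the rate is reported descriptively with no success claim.

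Use subjects as the unit in both sections. This matches the primary outcome definition and the benchmark in section 6.1, and the bracket settles how a two-level subject is counted.

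There are two acceptable alternatives. If the sponsor already has a written criterion, carry its number, statistic and unit into both sections. If it wants no formal criterion, delete the success sentence and report the estimate and interval only.

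The edit is short, but the lower-limit rule has a cost that the plan should state. It turns an approximate literature range into a firm goal. At n = 100, it declares success about 58% of the time at a true 88% and about 80% at a true 90%. Holding at least 80% power at a true 88% would take about 184 evaluable subjects: the pass mark is 0.80 + 1.96 × √(0.16/184) = 0.858, or 158 of 184, with exact power of 84%. Deleting the sentence leaves the sample size unaffected.

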9.2. Secondary Outcomes

Continuous variables, such as baseline demographics and change in patient-reported outcomes from preoperative baseline to 12 months, will be summarized using mean, standard deviation, minimum and maximum values. Paired t-test or a non-parametric equivalent (if data does not satisfy assumptions of normality) will be used to determine if changes in VAS or ODI scores are statistically significant from preoperative baseline to 12 months (+/- 3 months) follow-up. Responder analyses for changes in patient-reported outcomes at 12 months (+/- 3 months) will be conducted using minimum clinically important differences (MCID). Significant clinical improvements from preoperative baseline to 12 months (+/- 3 months) follow-up will be determined on a per-patient basis using the following MCID values:

- Improvement in ODI \geq 10 points [Ostelo et al. 2008]
- Improvement in VAS leg pain \geq 15 points [Ostelo et al. 2008]
- Improvement in VAS back pain \geq 15 points [Ostelo et al. 2008]

The proportion of patients with improvements exceeding the MCID values will be summarized as a percentage and 95% confidence interval.

Sub-group analyses will be performed based on the implant version (split-shim vs. "Version B"), history of previous surgery at the index level, patient co-morbidities, and demographic variables.

For any adverse events, the observed rate of each type of event will be summarized as a percentage with the 95% confidence interval and compared with rates observed in

	Clinical Protocol	Doc: CP-00001	Rev C
	Transforaminal/Posterior Lumbar Interbody Fusion with the FlareHawk® Expandable Interbody Fusion Device: A Retrospective Chart Review Study	Page 6 of 6	

the literature describing the current state of the art with other PLIF and TLIF interbody cages.

10. ATTACHMENTS:

Attachment A - Clinical Investigation Plan, Transforaminal/Posterior Lumbar Interbody Fusion with the FlareHawk® Expandable Interbody Fusion Device:
A Retrospective Chart Review Study, Protocol Date July 18, 2019, V1

